5.7. Other Analyses

5.7.1. Other Variables and/or Parameters

5.7.1.1. PK

5.7.1.1.1. PK samples

Blood samples will be collected to characterize the PK profile of encorafenib and its metabolite (LHY746) on the first day of treatment (Cycle 1 Day 1) and at steady state after 1 month treatment (Cycle 2 Day 1). Serial blood samples will be taken predose and 1 (± 10 minutes), 2 (± 10 minutes), 4 (± 30 minutes) and 6 (± 30 minutes) hours postdose on both days.

5.7.1.1.2. Non-compartmental PK Analysis

Encorafenib and LHY746 concentrations will be transmitted by the bioanalytical laboratory to

PII

PK analyses will be performed on the PK Set.

The following PK parameters for encorafenib and its metabolite LHY746 will be determined where possible using non-compartmental methods in the validated software program Phoenix WinNonlin (Certara, Version 8.1 or higher):

Parameter	Definition
AUC ₀₋₆	area under the concentration-time curve from time 0 to 6 hours post dose
AUC _{0-t_{last}}	area under the concentration-time curve from time 0 to the time of the last quantifiable concentration (t _{last})
C _{max}	maximum observed concentration
t _{max}	time of the maximum observed concentration
C _{min}	minimum observed concentration following multiple dosing (taken as the predose concentration on Cycle 2 Day 1) – determine for Cycle 2 Day 1 only
C _{last}	last quantifiable concentration
t _{last}	time of last quantifiable concentration
AR _{AUC}	observed accumulation ratio based on AUC ₀₋₆
MR _{AUC}	metabolite: parent ratio based on AUC ₀₋₆

Additional PK parameters may be determined where appropriate.

Sponsor Name: Pierre Fabre Médicament

Sponsor Protocol ID: W00090GE102

PII

During the study, a preliminary PK analysis will be carried out after 3 first participants, using the theoretical blood sampling times (planned time or scheduled time) and the validated concentration data. After the data base lock, the final PK analysis will be carried out using the validated concentrations data and the actual blood sampling times postdose where possible. If an actual time is missing, nominal time (i.e. theoretical time) will be assigned to the sample concentration.

The parameters C_{\max} , C_{\min} , C_{last} , t_{last} and t_{\max} will be obtained directly from the concentration-time profiles. If C_{\max} occurs at more than 1 timepoint, t_{\max} will be assigned to the first occurrence of C_{\max} .

All AUC values will be calculated using the linear trapezoidal rule for increasing concentrations and the logarithmic rule for decreasing concentrations (linear up/log down rule).

AR_{AUC} will be derived by dividing AUC_{0-6} from Cycle 2 Day 1 by AUC_{0-6} from Cycle 1 Day 1.

MR_{AUC} will account for differences in molecular weights (MW) between LHY746 and encorafenib using the formula: $MR_{\text{AUC}} = (LHY746 \text{ AUC} / LHY746 \text{ MW}) / (encorafenib \text{ AUC} / encorafenib \text{ MW})$

Encorafenib MW = 540

LHY746 MW = 424.88

5.7.1.1.2.1. Criteria for Handling Concentrations Below the Limit of Quantification

Handling of PK concentrations below limit of quantification (BLQ) will be applied as follows:

Type of analysis	Substitution value if BLQ occurs:		
	Before t_{\max}	After t_{\max} & between 2 quantifiable concentrations	After t_{\max} & NOT between 2 quantifiable concentrations
PK Non-compartmental analysis	0	Missing	Missing
Descriptive statistics	0	0	0
Plotting of individual data	0	Missing	Missing
Listing of individual data	BLQ	BLQ	BLQ

If an entire concentration-time profile is BLQ, it will be excluded from PK analysis.

If a predose concentration on Cycle 1 Day 1 is missing, it will be set to zero by default for PK analysis.

Sponsor Name: Pierre Fabre Médicament

Sponsor Protocol ID: W00090GE102

PII

5.7.1.2.2. Treatment of Outliers in PK Analysis

If a value is considered to be anomalous due to being inconsistent with the expected PK profile, it may be appropriate to exclude the value from the PK analysis. However, the exclusion of any data must have strong justification and will be documented in the CSR.

Any quantifiable predose concentration value on Cycle 1 Day 1 will be considered anomalous and set to missing for the PK analysis.

5.7.1.2.3. Criteria for Calculation of AUC

The minimum requirement for the calculation of AUC values will be the inclusion of at least three consecutive plasma concentrations above Lower Limit Of Quantification (LLOQ). If there are only 3 consecutive concentrations, at least one should follow C_{max} .

5.7.1.1.3. Presentation of PK Data

- Preliminary analysis

Preliminary individual PK encorafenib and LHY746 parameters will be listed.

Individual concentration-time profiles will be presented graphically for encorafenib and LHY746 on both linear and semi-logarithmic scales.

Only Phoenix WinNonlin outputs could be used at this stage. No statistical analysis on concentrations and PK parameters will be done.

- Final analysis

All encorafenib and LHY746 plasma concentrations will be listed by cycle and summarised by cycle for each analyte.

Listing of samples collection and concentrations will be provided on SAF, where participants excluded from PK Set will be flagged (**).

Listing of PK parameters will be provided on PK Set.

Figures and tables will be provided on PK Set.

In all listings, participants excluded from DDS will be flagged (*).

If the actual time of sample collection deviates from the nominal time by more than $\pm 10\%$, the concentration will be flagged and excluded from the descriptive statistics. Individual concentrations deemed to be anomalous will be flagged in the listings, with the reason for exclusion footnoted, and excluded from the descriptive statistics.

Sponsor Name: Pierre Fabre Médicament

Sponsor Protocol ID: W00090GE102

PII

PK concentrations will be summarised by cycle for each analyte using the description statistics: geometric mean, geometric coefficient of variation (CV%), arithmetic mean, arithmetic standard deviation (SD), median, minimum, maximum, number of observations (n), and number of participants (N). The following rules will apply for summarising of PK concentrations:

- At least 3 evaluable data ($N \geq 3$), otherwise only the minimum and the maximum are displayed and other statistics are indicated as "Not Applicable" (NA)
- Values that are BLQ will be set to 0 for the calculation of descriptive statistics.
- Arithmetic mean or median values that are BLQ will be presented as 0.
- If any BLQ results (treated as 0) are in a series of summarized data, geometric mean and CV% of geometric mean will be reported as not calculated (NC).

PK parameters will be listed by cycle and summarised by cycle for each analyte using the description statistics: geometric mean, geometric coefficient of variation (CV%), arithmetic mean, arithmetic standard deviation (SD), median, minimum, maximum, number of observations (n), and number of participants (N), with the exception of t_{max} and t_{last} where only N, n, median, minimum and maximum will be presented.

For derived PK parameters, descriptive statistics are calculated according to the following rules:

- at least 3 evaluable data ($N \geq 3$) are available, otherwise only the N, n, minimum and the maximum are presented and other statistics are shown as NA

Participant's encorafenib and LHY746 PK concentrations and parameters will be flagged and excluded from descriptive statistics if:

- vomiting occurs within the first 4 hours postdose on Cycle 1 Day 1 and Cycle 2 Day 1
- vomiting episode occurs within the first 4 hours postdose on the day of the last encorafenib dose prior to collection of PK samples (i.e. relating to the day before Cycle 2 Day 1)
- a participant missed any encorafenib dose or dose reduced within the 3 days immediately prior or the day of Cycle 2 Day 1 PK sample collection (i.e. for PK parameters and concentrations)

Sponsor Name: Pierre Fabre Médicament

Sponsor Protocol ID: W00090GE102

PII

Individual and summary concentration-time profiles will be presented graphically for encorafenib and LHY746 on both linear and semi-logarithmic scales, using the following 3 types of plots:

- Graphical display of the concentration-time profiles (*spaghetti plot*) by overlaying individual profiles (using actual sampling times) and the median profile (using nominal sampling times) on linear and semi-logarithmic scales. Figure will be repeated by analyte (encorafenib and LHY746) and by cycle (Cycle 1 Day 1 and Cycle 2 Day 1). Participants excluded from statistical analysis will be flagged.
- Individual profiles are by-participants plots and will use the actual sampling times. Cycle 1 Day 1 and Cycle 2 Day 1 concentration-time profiles will be overlaid on the same plot. Figure will be repeated by analyte (encorafenib and LHY746). Participants excluded from statistical analysis will be flagged.
- Arithmetic mean concentration-time profiles with error (+/-SD) bars using the nominal sampling times. Cycle 1 Day 1 and Cycle 2 Day 1 concentration-time profiles will be overlaid on the same plot. Figure will be repeated by analyte (encorafenib and LHY746).

Linear and semi logarithmic plots will be displayed on the same page side by side as appropriate.

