Abbreviations: AE = adverse event; ALT = alanine aminotransferase; aPTT = activated partial thromboplastin time; AST = aspartate aminotransferase; β-HCG = beta human chorionic gonadotropin; BUN = blood urea nitrogen; CK = creatine kinase; CT = computed tomography; eCRF = electronic case report form; D=Day; ECG = electrocardiogram; ECOG = Eastern Cooperative Oncology Group; EOT = end of treatment; GGT = gamma glutamyltransferase; HBsAg = hepatitis B surface antigen; HIV = human immunodeficiency virus; INR = international normalised ratio; LDH = lactate dehydrogenase; MRI = magnetic resonance imaging; NCI CTCAE = National Cancer Institute Common Terminology Criteria for Adverse Events; PET = positron emission tomography; PT = prothrombin time; PK = pharmacokinetics; RBC = red blood cell; WBC = white blood cell; ULN = upper limit of normal												
[a] Except Cycle 1 Day 1, if visit is missed theoretical cycles dates (7 days ± 3) are kept constant irrespectively of whether the visit is done and/or the study treatment is administered or not. If a participant does not attend for CnD1 visit, the CnD1 assessments will still need to be performed (and shall be recorded on the unscheduled visit in the eCRF)												
[b] Following the 30-day safety follow up, when clinically appropriate, it is also recommended the participant be monitored with dermatologic examinations and chest CT scans for cutaneous and non-cutaneous secondary malignancies for up to 6 months after the last study treatment dose or until initiation of another antineoplastic therapy												
[c] Cycle 1 Day 1 refers to the day the participant receives the first dose of study treatment Day 1 of Cycle 2 and of each subsequent cycle corresponds to Day 29 of the previous cycle												

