	Day -28 to -1										+ 7 days after EOT visit/last dose if EOT not performed

[m] Pregnancy test At baseline and EOT visit: serum b-HCG for women of childbearing potential only During treatment phase: urine pregnancy test for women of childbearing potential only
											

[n] Tumor assessment (MRI or CT scan). Tumor overall assessment (response, stable disease, progressive disease) will be determined locally by the investigator and reported in the eCRF along with the date of the radiological assessment: During treatment phase: radiological assessments should be performed at least every two cycles (8 weeks) ± 7 days for the first 12 months, then at least every three cycles (12 weeks) ± 7 days until disease progression. More frequent radiological assessments may be performed if needed At EOT visit: if the previous tumor assessment has been performed less than 30 days, there is no need to repeat the tumor assessment
											

[o] ECG: three serial ECGs conducted within approximately 5 to 10 minutes total time after at least 5 minutes rest. When an ECG is to be performed at the same time point as a blood collection, the ECG should be performed first
											

[p] Serial PK sampling will be collected at pre-dose, and 1, 2, 4, 6 hours post-dose on Cycle 1 Day 1 and Cycle 2 Day 1 only
											

2. Introduction

Encorafenib (Braftovi®; also known as PF-07263896, W0090, LGX818 or ONO-7702) is currently being developed in combination with binimatinib (Mektovi®), for the treatment of adult patients with metastatic melanoma and metastatic non-small cell lung cancer (NSCLC), who are B-RAF proto-oncogene, serine/threonine kinase (BRAF)- and mitogen-activated protein kinase (MEK)-inhibitor treatment-naïve and are either previously untreated or treated with one line of prior therapy in the metastatic setting.

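### The PK exclusions in SAP 5.7.1.1.3 are not limited to the affected PK day, so an event near Cycle 2 Day 1 can also remove a valid Cycle 1 Day 1 profile from the descriptive statistics

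*SAP*

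**What the plan says.** SAP 5.7.1.1.3 (Presentation of PK Data) opens the rule with "Participant's encorafenib and LHY746 PK concentrations and parameters will be flagged and excluded from descriptive statistics if" and then lists three triggers:

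- Early vomiting on the PK days: "vomiting occurs within the first 4 hours postdose on Cycle 1 Day 1 and Cycle 2 Day 1".
- Early vomiting on the day of the last dose before PK sampling, which the SAP explains as the day before C2D1.
- A missed or reduced dose: "a participant missed any encorafenib dose or dose reduced within the 3 days immediately prior or the day of Cycle 2 Day 1" sampling. A closing bracket adds that this covers parameters and concentrations. It names data types, not a day.

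The surrounding text points both ways on the unit of exclusion. For summaries, "PK parameters will be listed by cycle and summarised by cycle for each analyte using the description statistics". For the overlaid and individual plots, "Participants excluded from statistical analysis will be flagged".

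Full statistics require at least three evaluable values. For parameters, "otherwise only the N, n, minimum and the maximum are presented and other statistics are shown as NA". For concentrations below that number, the minimum and maximum are shown.

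Protocol Table 1, footnote [p], restricts serial sampling to predose and 1, 2, 4 and 6 "hours post-dose on Cycle 1 Day 1 and Cycle 2 Day 1 only". Protocol 4.1.1 and SAP 1.2 stop enrolment at three participants if none of them has a DLT.

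**The concern.** The C1D1 profile is a single-dose profile, complete about four weeks before the C2D1 look-back begins. A dose missed on Day 27, or vomiting on Day 28, cannot change it. There is no pharmacokinetic reason for such an event to remove C1D1 values from the C1D1 summary, but a programmer who follows the sentence as written would remove them.

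The study may finish with three participants, which is also the SAP's minimum for full statistics, so one unnecessary exclusion is enough to blank most of the C1D1 table. PK after single and repeated administration is a named secondary endpoint (Protocol section 3, SAP 1.1), and the single-dose summary would be reduced for a reason unrelated to that day.

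If the point is left open, the choice between readings will be made when only a handful of profiles exist and their values are visible.

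**Working it through.** The documents give no PK sample-size or precision figure to reproduce. The sample size is stated to be empirical (Protocol 9.2, SAP 3). The check is a count against the minimum-N rule, followed by a scenario calculation.

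**Step 1. Can the trigger occur in a participant who is not replaced?**
- Planned Cycle 1 dose (SAP 5.6.1): 28 × 300 mg = 8400 mg, which agrees with the SAP's figure.
- Evaluability without a DLT requires at least 75% of this: 0.75 × 8400 = 6300 mg.
- In full doses: 6300 / 300 = 21, so up to 28 − 21 = 7 doses can be missed.
- Day 1 of Cycle 2 corresponds to Day 29 (Table 1, footnote [c]), so the three days before it are Days 26 to 28. A participant could miss all three, remain evaluable and not be replaced.

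**Step 2. Effect of one C2D1-type event when three participants have PK data.**

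| | Literal reading (whole participant) | Reading by PK day |
|---|---|---|
| C1D1 | N = 3 − 1 = 2, reduced statistics | N = 3, full statistics |
| C2D1 | N = 2, reduced statistics | N = 2, reduced statistics |
| AR_AUC (C2D1 AUC0-6 / C1D1 AUC0-6) | N = 2 | N = 2 |

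Only the C1D1 row differs. That row is the whole effect of the wording.

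**Step 3. Dependence on the number with PK data.** After one exclusion, n = 4, 5 or 6 leaves 3, 4 or 5, and full statistics are kept. The loss after a single event is specific to n = 3.

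**Step 4. Chance that C1D1 falls below three under the literal reading.** Let p be the chance that a participant has an event in the C2D1 look-back. It is assumed, taken as equal across participants and independent between them. Statistics are lost when at least n − 2 participants are excluded.

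- n = 3: P = 1 − (1 − p)³. For p = 0.05, 1 − 0.8574 = 0.143. For p = 0.10, 1 − 0.729 = 0.271. For p = 0.20, 1 − 0.512 = 0.488.
- n = 4: P = 1 − (1 − p)⁴ − 4p(1 − p)³. For p = 0.10, 1 − 0.6561 − 0.2916 = 0.052.
- n = 5 and n = 6 use the corresponding binomial upper tails.

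| p (assumed) | n = 3 | n = 4 | n = 5 | n = 6 |
|---|---|---|---|---|
| 5% | 14.3% | 1.4% | 0.12% | 0.01% |
| 10% | 27.1% | 5.2% | 0.86% | 0.13% |
| 20% | 48.8% | 18.1% | 5.8% | 1.7% |

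Under a day-specific rule, C2D1 events contribute nothing to C1D1 loss. This is true by construction, so it is not a separate finding.

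**The case against.** The strongest reply is that the SAP never expressly says both days are dropped. Summaries are by cycle, two triggers are tied to C2D1, and other exclusions in the same section act on single concentrations (mistimed or anomalous samples). A sensible programmer might apply the rule by day. This stands in part: a per-day reading is available. But it has to be inferred, because the sentence names the participant's data without limit and the plot text also speaks of excluded participants. The sample-level exclusions show that the SAP writes a narrow rule when it means one.

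Four stronger conclusions are tempting, and the documents do not support them:

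- **That no PK summary is left.** Below three values, the SAP still shows the minimum and maximum (plus N and n for parameters). The exclusion applies to descriptive statistics only, so listings and flagged individual plots still carry the data.
- **That the wording also causes the C2D1 loss.** A missed or reduced dose before C2D1 leaves N=2 of 3 on that day under either reading, and the proposed fix does not change this.
- **That the first trigger needs vomiting on both PK days.** Protocol 8.6.1 uses the same pairing of days when it asks for the vomiting time, and then refers to that day. The conjunction is probably meant distributively. It deserves tidying but is not a separate error.
- **That the C2D1 samples should move to a later cycle when the look-back fails.** Cycle dates "are kept constant irrespectively of whether the visit is done and/or the study treatment is administered or not", so a participant on hold may give C2D1 samples that are then left out of the summaries. But moving them needs a protocol amendment and makes steady state mean different cycles for different participants. In a participant whose dose stays reduced, it would still not give a 300 mg profile. This is a debatable trade-off and is not recommended here.

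It is also fair to say that the PK Set (SAP 4.3) takes any dosed participant with one postdose result. It can therefore exceed three if a non-evaluable participant is replaced, and the problem shrinks quickly as Step 3 shows.

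**Conclusion.** The point holds as a wording defect with a limited but avoidable consequence. As written, the rule does not confine PK exclusions to the affected day. Followed literally, it removes C1D1 data because of events that cannot have influenced them. With exactly three participants with PK data, one event reduces the C1D1 summary to the minimum and maximum (plus N and n for parameters). The chance is about 14%, 27% or 49% for p of 5%, 10% or 20%.

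These figures rest on the literal reading, on n = 3, on independence between participants, and on values of p that are assumptions. The size is therefore conditional, but the correction does not depend on it: under no value of p is there a reason to drop C1D1 data for a C2D1 event. The wording should be corrected before database lock. The primary endpoint and the safety analyses are unaffected.

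**What to change.** Rewrite the three triggers in SAP 5.7.1.1.3 by PK day:

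- Vomiting within 4 hours after the C1D1 dose excludes that participant's C1D1 concentrations and parameters.
- Vomiting within 4 hours after the C2D1 dose, or after the dose on the preceding dosing day, excludes C2D1 concentrations and parameters only.
- A missed or reduced dose in the C2D1 look-back excludes C2D1 concentrations and parameters only.
- AR_AUC is excluded if either day is excluded.

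If the first bullet is kept as one line, replace the word and between the two days by or, followed by respectively, so that it matches Protocol 8.6.1. In the plot rules, flag the excluded profile (participant and PK day) rather than the participant.

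The cost is a few lines of SAP text and the matching programming specification. No protocol amendment, visit, sample or procedure is added. The C2D1 summary will still fall below three values if one of three participants has an event, and the report should say so.

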5.7.2. Subgroup Analyses

Not Applicable due to the low number of participants to be included in the study

5.8. Interim Analyses

There are no interim analyses planned.

5.8.1. Trial Steering Committee (TSC)

The TSC will analyze the available safety data in order to evaluate the tolerability of encorafenib 300 mg QD.

The TSC will assess any toxicities as significant or not once the first three participants (and six participants if required) have fully completed the first cycle of treatment (28 days). The tolerability assessment will be based on the DLT rate (DLTs observed in <33% of participants) and evaluation of the overall toxicity profile (based on deaths, treatment emergent SAEs, TEAEs leading to discontinuation and to dose interruption/reduction). The TSC will make a recommendation if the dose of encorafenib is not deemed tolerable.

The TSC membership, data to be reviewed, timing of the planned reviews as well as the operating procedures will be described in the TSC Charter.

6. Supporting Documentation

6.1. Appendix 1: List of Abbreviations

Abbreviation	Definition
Ab	Antibody
AE	Adverse Event
AESI	Adverse Event of Special Interest
ALP	Alkaline Phosphatase
ALT	Alanine Aminotransferase
aPTT	activated Partial Thromboplastin Time
AST	Aspartate Aminotransferase
ANC	Absolute Neutrophil Count
ATC	Anatomical Therapeutic Classification
AUC	Area Under the Curve
BLQ	Below the Level of Quantification
BRAF	B-RAF Proto-oncogene, Serine/threonine Kinase
BRAF V600E	B-RAF Proto-oncogene, Serine/threonine Kinase V600E Mutant
BRAF wt	B-RAF Proto-oncogene, Serine/threonine Kinase Wild Type
BMI	Body Mass Index
CI	Confidence Interval
C _{last}	Last quantifiable concentration
C _{max}	Maximum Concentration
C _{min}	Minimum Concentration
CrCl	Creatinine Clearance

Sponsor Name: Pierre Fabre Médicament

Sponsor Protocol ID: W00090GE102

PII

CT	Computed Tomography
CTCAE	Common Terminology Criteria for Adverse Event
DBP	Diastolic Blood Pressure
DDS	Dose-Determining Set
DI	Dose Intensity
DILI	Drug-Induced Liver Injury
DLT	Dose-Limiting Toxicity
DNA	Deoxyribonucleic Acid
ECG	Electrocardiogram
ECOG	Eastern Co-operative Oncology Group
eCRF	Electronic Case Report Form
EGFR	Epidermal Growth Factor Receptor
EMA	European Medicines Agency
FDA	US Food and Drug Administration
FSH	Follicle Stimulating Hormone
GGT	Gamma Glutamyl Transferase
HBsAg	Hepatitis B Surface Antigen
HBV	Hepatitis B Virus
HCV	Hepatitis C Virus
HIV	Human Immunodeficiency Virus
INR	International Normalized Ratio
LDH	Lactate Dehydrogenase
LFT	Liver Function Test
LLN	Lower Limit of Normal

Sponsor Name: Pierre Fabre Médicament

Sponsor Protocol ID: W00090GE102

PII

LLoQ	Lower Limit of Quantification
MedDRA	Medical Dictionary for Regulatory Activities
MEK	Mitogen-activated Protein Kinase Kinase
MRI	Magnetic Resonance Imaging
NCI	National Cancer Institute
NCI CTCAE	National Cancer Institute Common Terminology Criteria for Adverse Event
NMPA	National Medical Products Administration
NSCLC	Non-small Cell Lung Cancer
PDI	Planned Dose Intensity
PK	Pharmacokinetic
PO	Per Oral
PT	Preferred Term
QD	Once Daily
RBC	Red Blood Cells
RDI	Relative Dose Intensity
RP2D	Recommended Phase 2 Dose
RNA	Ribonucleic Acid
SAE	Serious Adverse Event
SAF	Safety Set
SAP	Statistical Analysis Plan
SAS®	Statistical Analysis Software
SBP	Systolic Blood Pressure
SI	System International
SOC	System Organ Class

Sponsor Name: Pierre Fabre Médicament

Sponsor Protocol ID: W00090GE102

PII

SMQs	Standardized MedDRA Queries
TBL	Total Bilirubin
TEAE	Treatment Emergent Adverse Event
TFL	Tables Figures and Listings
t_{last}	Time of last quantifiable concentration
t_{max}	Time of the maximum observed concentration
TOC	Table Of Contents
TSC	Trial Steering Committee
ULN	Upper Limit of Normal
WBC	White Blood Cells
WHO	World Health Organization

